### **2.4.5.3 Deaths**

The following summaries of deaths will be generated for the safety population:

- TEAE leading to death (death as an outcome on the AE case report form page as reported by the Investigator) during the on-treatment period by primary SOC, HLG, HLT, and PT showing number (%) of participants (Safety population)
- AE leading to death (death as an outcome on the AE case report form page as reported by the Investigator) during the 56-week on-study observation period by primary SOC, HLG, HLT, and PT showing number (%) of participants (Safety population)

- Number (%) of participants who died by study period (on-study period (on-treatment period, post-treatment period), post-study period)
- Pre-treatment AEs, TEAEs and post-treatment AEs leading to death (death as an outcome on the AE case report form page as reported by the Investigator) by study period (pre-treatment period, on-treatment period, and post-treatment period) showing number (%) of participants

#### **2.4.5.4 Analyses of laboratory variables**

All hematology and clinical chemistry results will be listed by treatment group, participants and visit, including scheduled and unscheduled/repeat measurements.

The summary statistics (including number, mean, median, standard deviation, minimum and maximum) of all protocol-required laboratory variables (central laboratory values and changes from Baseline) will be calculated for each scheduled visit and last value on treatment by treatment group. This section will be organized by biological function as specified in [Section 2.1.4.3](#).

The incidence of PCSAs at any time during the on-treatment period will be summarized by biological function and treatment group whatever the Baseline level and/or according to the following Baseline status categories:

- Normal/missing
- Abnormal according to PCSA criterion or criteria

For parameters for which no PCSA criteria are defined, similar table(s) using the normal range will be provided. For calcitonin, no PCSA criterion is defined. Similar summaries will be provided using the pre-defined categories:  $\leq$ ULN,  $>$ ULN -  $<$  20 ng/L,  $\geq$ 20 -  $<$ 50 ng/L, and  $\geq$ 50 ng/L (Note that ng/L is the standard international unit and is equivalent to pg/mL).

All measurements collected during the on-treatment period, including values from unscheduled visits, will be considered for the PCSA summaries. These summaries will include participants in the safety population who have at least 1 assessment performed during the on-treatment period. When a PCSA definition involves only a change from baseline value, participants must also have a baseline value to be included in the summaries, and when required by the definition of the abnormality, participants must also have available laboratory normal ranges.

For some parameters, such as liver enzymes, the lower limit of normal (LLN) is not considered clinically relevant, and values below this limit are considered normal. When there are multiple PCSA criteria for a specific parameter (eg, ALT), the participant will be counted once during the on-treatment period for the specific parameter in question under the worst/maximum PCSA category.

Elevated liver parameters will be summarized by treatment group in safety population.

For PCSA, both central and local lab data will be used.

A listing of participants with at least 1 post-baseline PCSA (or out of normal range when no PCSA criterion is defined) will be provided and will display the entire participants' profile across time for all parameters belonging to the corresponding biological function. Individual data listings will include flags when applicable:

- Baseline values will be flagged "B".
- Normal laboratory ranges, available for most laboratory parameters, will be identified as ULN and LLN. Baseline, and individual data will be flagged "L" if the value is below the LLN and will be flagged "H" if it is above the ULN.
- Laboratory PCSA criteria will be used for the corresponding laboratory parameters. Values reaching a PCSA limit will be flagged (+, ++, -, or – depending upon the direction and level of the abnormality). Flags for WBC and differential counts will be determined using data expressed in international units.

For parameters whose PCSA criteria are multiples of the ULN, the parameter's value will also be expressed as a multiple of the ULN in the individual data provided.

#### **2.4.5.5 Analyses of vital sign variables**

The summary statistics (including number, mean, median, standard deviation, minimum and maximum) of all vital sign variables will be calculated for each scheduled visit by treatment group.

The incidence of PCSAs at any time during the on-treatment period will be summarized by treatment group irrespective of the Baseline level and/or according to the following Baseline status categories:

- Normal/missing
- Abnormal according to PCSA criterion or criteria

A listing of participants with at least 1 post-baseline PCSA will be provided and will display the participant's profile over time of all vital sign parameters. Individual data listings will include the following flags:

- Baseline values will be flagged "B",
- Parameter values reaching a PCSA limit will be flagged (+, or - depending of the direction).

#### **2.4.5.6 Analyses of electrocardiogram variables**

The frequency and percentage of 12-lead ECG interpretation (normal, abnormal) will be provided at each scheduled visit by treatment group.

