### 8.2.3 Electrocardiograms

A 12-lead ECG recording will be performed locally as scheduled in the SoA (see [Section 1.3](#)).

The 12-lead ECG should be performed after the participant has been in the supine position for at least 10 minutes and prior to other study procedures at that visit (eg, blood collection, IMP administration). The Investigator should review the ECG trace and document the interpretation, sign and date the ECG printout, and record it in the eCRF. Each ECG trace must be analyzed in comparison with the baseline ECG results. All original ECG traces must be kept as source data. The ECG assessment of "normal" or "abnormal" will be analyzed.

Note: Any new ECG abnormality should be rechecked for confirmation and reported as an AE if considered clinically significant by the Investigator.

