**Table 6 - Safety analyses**

Endpoint	Statistical Analysis Methods
AEs	
All AEs will be coded to an LLT, PT, HLT, and HLGT and associated SOC using the version of MedDRA currently used by the Sponsor at the time of database lock.
 
Adverse event incidence table will be presented by primary SOC (sorted by internationally agreed order), HLGT, HLT, and PT (sorted in alphabetical order) for each treatment group, showing the number (n) and percentage (%) of participants who experienced an AE.
 
Adverse event incidence table will be provided by treatment group for all types of TEAEs: all TEAEs, all treatment-emergent SAEs, all TEAEs leading to permanent treatment discontinuation, and all TEAEs leading to death.
 
The AE, SAE, and AE leading discontinuation table will also be presented for the on-study period.

Hypoglycemia	
The number (%) of participants with at least 1 hypoglycemic event during the on-treatment period will be assessed per type of hypoglycemic event (see Section 8.2.5) and according to time of occurrence (nocturnal [ie, 00:00 to 05:59 am], daytime [ie, 06:00 am to 23:59]). Documented hypoglycemia (symptomatic or asymptomatic) will be also evaluated for the more stringent SMPG threshold of <3.0 mmol/L (<54 mg/dL).
 
Summaries will be presented overall and by type of event for each treatment group.
 
The total number of events (per participant-years) will be computed and summarized overall and by type of event for each treatment group.

Vital signs and laboratory data	
For quantitative safety parameters based on central laboratory/reading measurements, descriptive statistics will be used to summarize results and change from baseline values by visit and treatment group.

ECG	
The incidence of PCSA, defined as abnormal values considered medically important by the Sponsor according to predefined criteria/thresholds based on literature review, will be summarized at any time during the on-treatment period.
 
Results will be presented both in standard international and conventional US units
 
The incidence of normal and abnormal ECG status at any time during the on-treatment period will be summarized by treatment group whatever the baseline level and according to baseline status.

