#### **2.1.4.5 Electrocardiogram variables**

ECG variables will include 12-lead ECG interpretation (normal/abnormal) provided by the investigator. 12-lead ECG recording will be performed locally at Randomization, Week 12 and Week 56. Investigator's interpretation of normal and abnormal will be reported in the eCRF.

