#### **2.5.5 Unscheduled visits**

Unscheduled visit measurements of laboratory data, vital signs, and ECG will not be included in the by-visit summaries, but will be used for computation of Baseline and PCSAs.

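### The SAP reduces the protocol's any-time, by-baseline-status ECG summary to by-visit counts without recording the change, so new-onset ECG abnormality is not tabulated as such

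*SAP*

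**What the plan says.** **Protocol.** The ECG entry in Table 6 (Section 9.4.2) reads "The incidence of normal and abnormal ECG status at any time during the on-treatment period will be summarized by treatment group", and continues "whatever the baseline level and according to baseline status". So it asks for an any-time incidence and for a split by baseline status. Section 8.2.3 tells the investigator how to read the tracing: "Each ECG trace must be analyzed in comparison with the baseline ECG results".

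**SAP.** Section 2.1.4.5 defines the data: "ECG variables will include 12-lead ECG interpretation (normal/abnormal) provided by the investigator". The schedule follows: "12-lead ECG recording will be performed locally at Randomization, Week 12 and Week 56". The whole of Section 2.4.5.6 is "The frequency and percentage of 12-lead ECG interpretation (normal, abnormal) will be provided at each scheduled visit by treatment group". It specifies no any-time incidence, no baseline split and no ECG listing. Section 2.5.5 adds "Unscheduled visit measurements of laboratory data, vital signs, and ECG will not be included in the by-visit summaries"; such recordings are kept only for deriving baseline and PCSAs. The general safety rules in Section 2.4.5 and Appendix B name ECG among the PCSA parameters.

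The neighbouring sections on laboratory data (2.4.5.4) and vital signs (2.4.5.5) keep the any-time structure and provide for baseline categories. Table 1 in SAP Section 1.6 lists the changes made in version 2. The ECG reduction is not among them.

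**The concern.** A by-visit percentage is a prevalence. It does not say whether the abnormal readings at Week 12 or Week 56 come from people who were normal at baseline. The protocol's two features, any-time counting and the split by baseline status, are what turn an ECG reading into an incidence of new abnormality, and both are missing from the SAP.

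The treatment of unscheduled ECGs adds to this. The protocol generates them: new abnormalities are rechecked (8.2.3), and a participant about to start rescue attends an unscheduled visit with the end-of-treatment assessments (6.1.2.2), which include a 12-lead ECG in the Schedule of Activities. An abnormality first seen on such a recording is outside the only ECG table specified.

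At stake is a descriptive safety output. No hypothesis test, analysis population or efficacy conclusion depends on it.

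**Working it through.** The plan states no figure here to reproduce. The check compares the texts, then asks what by-visit counts can identify.

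**1. Text comparison.**

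| Feature | Protocol Table 6 | SAP 2.4.5.6 with 2.5.5 |
|---|---|---|
| Unit | any time on treatment | each scheduled visit |
| Baseline status | overall and split | baseline is one column; no cross-classification |
| Post-baseline unscheduled ECGs | not excluded | excluded from by-visit tables |

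**2. The PCSA route.** The ECG criteria in Appendix B use heart rate, PR, QRS, QT and QTc. The only ECG variable defined in 2.1.4.5 is the investigator's reading, and 2.4.5.6 specifies no ECG PCSA table. So a post-baseline unscheduled ECG is sent to an analysis that the defined data cannot feed.

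**3. What the by-visit counts identify.** Inputs: N = 300 per arm (SAP 1.3) and complete data. Assumed: a share r reads abnormal at baseline, at Week 12 and at Week 56. The documents give no value for r, so a range is shown. Let b = N × r.

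- Baseline-normal participants: N − b.
- Fewest newly abnormal at either later visit: 0, when the same b people are abnormal throughout.
- Most newly abnormal: min(N − b, 2b), when all later abnormal readings come from baseline-normal people and the two visits do not overlap.

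| r | b | N − b | Newly abnormal, range | Share of baseline-normal |
|---|---|---|---|---|
| 10% | 30 | 270 | 0 to 60 | 0% to 22.2% |
| 20% | 60 | 240 | 0 to 120 | 0% to 50.0% |
| 30% | 90 | 210 | 0 to 180 | 0% to 85.7% |

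These are logical limits, not likely values. They show that one set of by-visit counts fits very different numbers of new abnormalities.

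**4. The role of reversion.** Assume 25% abnormal at baseline, and new abnormality in 4% versus 8% of baseline-normal participants.

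- No reversion: 0.25 + 0.75 × 0.04 = 0.28 and 0.25 + 0.75 × 0.08 = 0.31. With the baseline column present, the rises are 3 and 6 points, so the doubling is visible.
- With reversion in the second arm only: the 3-point gap closes if 0.03 / 0.25 = 12% of that arm's baseline-abnormal participants read normal later. Both arms then show 28%, while new onset is still 4% versus 8%.

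The by-visit table is therefore enough only if abnormal readings persist. A table by baseline status does not need that assumption.

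**The case against.** The case for leaving this alone has several sound parts.

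- **The baseline column is there.** Randomization is a scheduled ECG visit. A reader might infer that the planned table cannot show a doubling of new abnormality. Step 4 shows that it can when readings persist; it fails only under reversion or when different people are abnormal at different visits.
- **Adverse events.** A reader might infer that findings at unscheduled ECGs are lost entirely. They are not. Under Protocol 8.2.3 a new abnormality considered clinically significant is reported as an AE, and on-treatment AEs enter the TEAE tables of SAP 2.4.5.1. What goes untabulated is a new abnormality not reported as an AE.
- **Rechecks.** If the abnormality was first seen at a scheduled visit, it is already counted, and leaving out the confirmatory ECG costs nothing. Only first detection at an unscheduled recording is affected.
- **Heart rate.** The known class effect might seem to raise the stakes. Protocol 2.3 assigns heart-rate monitoring to vital signs, and SAP 2.4.5.5 analyses vital-sign PCSAs at any time on treatment. The ECG gap does not weaken that.
- **Pre-existing abnormality.** A reader might suppose that it dominates the counts. No baseline abnormal-ECG rate is given, so this cannot be claimed.
- **Wording and scale.** SAP 2.1.4.5 says what the ECG variables include, which may leave room for others; none is defined. Section 1.6 covers major changes, and a sponsor may not have counted this as one.

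These points limit the concern. They do not remove the mismatch with Protocol Table 6 or supply the missing cross-classification.

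**Conclusion.** The point holds as a minor correction. The SAP drops two features of a protocol-planned ECG summary without recording it, and what remains does not identify new-onset abnormality. The size in this trial cannot be computed, because the documents give neither the baseline abnormal rate nor the reversion rate. The illustrations rest on assumed rates, and the bounds also on 300 per arm with complete data. The practical loss is confined to new abnormalities not reported as AEs, including those first seen at unscheduled ECGs. That post-baseline unscheduled ECGs enter no specified ECG table rests on reading 2.1.4.5 as the full list of ECG variables. An unscheduled pre-dose ECG can still serve as baseline.

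**What to change.** In SAP 2.4.5.6, restore the Protocol Table 6 analysis: the number and percentage of participants with at least one abnormal ECG at any time in the on-treatment period defined in SAP 2.1.4, including unscheduled recordings. Present it by treatment group, overall and by baseline status (normal/missing, abnormal), as in the vital-sign section. Keep the by-visit table as supportive, and state in 2.5.5 that unscheduled ECGs count toward the any-time table.

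Reconcile the ECG PCSA references in 2.4.5, 2.5.5 and Appendix B with the data: either remove them for ECG or define the numeric ECG variables they need. If the reduced analysis is intended, enter the departure from Table 6 in the SAP change table with a reason.

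The cost is one descriptive table. Protocol 8.2.3 already has the readings recorded in the eCRF, so no new data collection is needed.

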### **2.4.5.7 Analyses of other safety endpoints**

#### **Anti-drug Antibody:**

An anti-drug antibody positive participant is defined as a participant with at least one treatment-induced or treatment-boosted ADA-positive sample at any time.

Summaries of ADA data will be provided for participants treated with efpeglenatide only. All summaries related to kinetics of ADA response (ADA status and magnitude, ADA attributes, participant status, ADA incidence) will be descriptive; no statistical significance tests will be performed on ADA data. The incidence of ADA status (positive/negative) will be summarized by visit, treatment, and individual titer for the ADA population. Incidence of treatment induced and treatment-boosted (treatment emergent) ADA during on-study period will be summarized by treatment. Incidence of participants with ADA cross-reactivity to endogenous GLP-1 (positive/negative), and to endogenous glucagon (positive/negative) will be summarized by visit and treatment. Incidence of participants with ADA directed against PEG linker, HMC001 moiety and exendin-4 moiety (positive/negative) will be summarized by visit and treatment.

Incidence of participants with neutralizing antibodies against efpeglenatide and against endogenous GLP-1 and Glucagon will be summarized by visit and treatment.

ADA data from unscheduled visits (due to SAE for example) will not be included in summary and will be presented only in ADA values listing.

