### **2.1.5 Immunogenicity endpoints**

#### **2.1.5.1 Anti-drug (efpeglenatide) antibody**

Blood samples are taken to assess the Anti-drug antibody (ADA) status (positive/negative) and level (titer). Mapping the ADA epitopes of confirmed positive samples to different moieties of efpeglenatide, (ie, HMC001, exendin-4 and polyethylene glycol (PEG)) and cross-reactivity to endogenous GLP-1 (positive/negative), endogenous glucagon (positive/negative), neutralizing capacity of ADAs will also be evaluated for efpeglenatide groups in serum, at the time points specified in protocol.

Subjects with pre-existing ADAs are those with a positive ADA at Baseline. Non-missing post-Baseline titer values are deemed treatment-induced ADAs if the subject had a negative or missing ADA status at Baseline. Treatment-boosted ADAs are defined as a post-Baseline minimum 2-fold increase in Baseline titer value for subjects with pre-existing ADA at Baseline.

Persistent ADA response is defined as: Treatment-induced or treatment-boosted ADA detected at two or more sampling time points during the study (ie, including post-study observation period), where the first and last treatment-induced or treatment-boosted ADA samples (irrespective of any negative samples in between) are separated by at least 16 weeks.

Transient ADA response is defined as: (1) Treatment induced or treatment-boosted ADA detected only at 1 sampling time point during the study (excluding the last sampling time point); or (2) Treatment induced or treatment-boosted ADA detected at 2 or more sampling time points during the study, where the first and last treatment-induced or treatment-boosted ADA samples (irrespective of any negative samples in between) are separated by a period less than 16 weeks and the last time point is ADA-negative.

Indeterminate ADA response is defined as: (1) Only the last sampling time point is positive; or (2) the last two samples, separated by a period less than 16 weeks are positive.

The data will be presented as:

- Number of participants by ADA status (positive/negative) at scheduled visits
- Number of participants with treatment-induced ADAs among the participants with ADA negative or missing at Baseline
- Number of participants with treatment-boosted ADAs among the participants with ADA positive at Baseline
- ADA titer at scheduled visits
- Number of participants by ADA cross-reactivity to endogenous GLP-1 (positive/negative) at scheduled visits

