### 2.3.3 ADA population

ADA population is defined as:

- All efpeglenatide participants from the safety population with at least 1 post-Baseline valid ADA sample after drug administration.

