- The frequency of TEAEs over time will be provided for nausea, vomiting and diarrhea, using weekly time intervals up to 56 weeks, ie, [0-1] week, [1-2] weeks, [2-3] weeks, [3-4] weeks, etc. In each time interval, the numerator in the calculation of percentages will be the number of participants with at least 1 TEAE occurring in this time interval. Two types of analyses will be included: (1) only the first event will be counted for each participant and all recurrent events will not be included, and the denominator for the calculation of percentages will be the number of participants at risk at the beginning of the time interval who did not experience a first event in the preceding intervals; and (2) the recurrent events in subsequent intervals will be counted once for each participant in the numerator of the corresponding interval, and the denominator for the calculation of percentages will be the number of participants at risk at the beginning of the time interval. A histogram of the frequency over time (by weekly intervals) will also be presented as appropriate.
- All TEAEs by BMI subgroup (< 30, ≥ 30 kg/m^2)
- All TEAEs by Anti-Efpeglenatide Antibody Status (Positive, Negative)

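### SAP 2.4.5.7 defines ADA positivity by a sample at any time but confines unscheduled ADA data to a listing, so treatment-emergent incidence can omit defined positives and ADA status in other tables is unclear

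*SAP*

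**What the plan says.** The anti-drug antibody part of SAP 2.4.5.7 opens with a participant-level rule: "An anti-drug antibody positive participant is defined as a participant with at least one treatment-induced or treatment-boosted ADA-positive sample at any time". It closes with a rule on data sources: "ADA data from unscheduled visits (due to SAE for example) will not be included in summary". The rest of that sentence sends these data to the listing of ADA values and nowhere else.

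Most summaries listed between these two sentences are by visit. One is not: "Incidence of treatment induced and treatment-boosted (treatment emergent) ADA during on-study period will be summarized by treatment".

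Three other places bear on the point:

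- **SAP 2.1.5.1** defines the sample-level term without regard to visit type: "Non-missing post-Baseline titer values are deemed treatment-induced ADAs if the subject had a negative or missing ADA status at Baseline". Treatment-boosted ADA, a rise of at least 2-fold over the baseline titer, is not tied to scheduled visits either.
- **SAP 2.3.3** admits to the ADA population any efpeglenatide participant in the safety population "with at least 1 post-Baseline valid ADA sample after drug administration".
- **Protocol Section 3, Table 1** counts participants with treatment-induced or treatment-boosted ADA over the study period, again with no limit to scheduled visits.

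ADA status is then used elsewhere. SAP 2.4.5.1 tabulates TEAEs by antibody status, and SAP 2.4.4.1 describes the Week 30 HbA1c change by treatment-emergent ADA status.

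**The concern.** A positive sample cannot both count whenever it is drawn and appear only in a listing. For by-visit tables the exclusion is ordinary practice. For a participant-level count over the whole study it overrides the stated definition, and the SAP does not say that this is intended.

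The SAP's own example of an unscheduled draw is one made because of an SAE, so the samples set aside are not a random subset. Severe allergic reactions, severe injection site reactions and severe immune complex disease are adverse events requiring specific monitoring. Protocol Table 7 plans to relate immunogenicity to safety and efficacy. If ADA status can be derived in two ways, two programmers can produce different incidence tables, and possibly different tables by ADA status, from the same data.

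**Working it through.** The plan states no figure to reproduce here. The check is a comparison of texts, followed by arithmetic on assumed counts.

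**1. Does the exclusion reach a participant-level table?** The last sentence of the ADA part refers to summaries without qualification, and the listing is the only destination it allows. The summaries in that part include treatment-emergent incidence by treatment over the on-study period. Literally read, the exclusion covers it.

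**2. Was a by-visit exclusion meant?** The SAP words such an exclusion clearly elsewhere. Section 2.5.5 removes unscheduled laboratory, vital-sign and ECG values from by-visit summaries but keeps them for baseline and for PCSAs. Sections 2.4.5 and 2.4.5.4 likewise count unscheduled values in PCSA tables that cover any time on treatment. The ADA part has no matching exception.

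**3. Trace one participant.** Suppose the baseline sample is negative, all scheduled samples (Weeks 4, 12, 30 and 56, and EOS) are negative, and one unscheduled sample is positive.

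| Rule | Result |
|---|---|
| ADA population (2.3.3) | included |
| Participant definition (2.4.5.7) | positive |
| By-visit ADA tables | negative at each scheduled visit, as expected |
| On-study treatment-emergent incidence, literal reading | in the denominator, not in the numerator |
| TEAEs by ADA status (2.4.5.1) | not stated |
| HbA1c change by ADA status (2.4.4.1) | not stated |

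A participant with no scheduled post-baseline sample would be in the ADA population with no summarised status at all.

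**4. Which samples are unscheduled?** SAE-driven draws are the SAP's example. Under the protocol's Schedule of Activities, the pre-rescue visit is also unscheduled and repeats the EOT assessments, and ADA is listed at EOT. For early treatment-discontinuation visits, SAP 2.5.4 gives rules for efficacy data only; it does not say how their ADA samples are classed.

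**5. Size, incidence.** Let N be the ADA population, P the number positive on scheduled samples, and k the number positive only on unscheduled samples. The literal rule reports P/N and the definition gives (P + k)/N, a shortfall of k/N. One participant is 1/300 = 0.33 percentage points in an arm of the planned size, or 1/600 = 0.17 points over both arms. Assume N = 600 and P = 30, so that P/N = 5.0%:

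- k = 1: 31/600 = 5.2%
- k = 3: 33/600 = 5.5%
- k = 6: 36/600 = 6.0%
- k = 12: 42/600 = 7.0%

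**6. Size, TEAE table, only if the exclusion is carried into it.** Assume 30 participants positive by the definition, 6 of them with the event: 6/30 = 20.0%. If 1, 2 or 3 of those 6 are classed as negative, the rate among positives becomes 5/29 = 17.2%, 4/28 = 14.3% or 3/27 = 11.1%.

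**7. The opposite bias.** Assume no true association, 10% positive on scheduled samples, and one extra draw that detects a further 5%. If participants with events get that extra draw and it counts, they show 10% + 5% = 15% positive against 10% in the others.

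**The case against.** The strongest reply is that the opening definition governs participant status and the last sentence is only a loosely worded rule for tables that are mostly by visit. That is a possible intention. It does not fit the restriction to the listing or the wording of SAP 2.5.5, and it leaves the on-study incidence unresolved.

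Other parts of the reply stand, and they limit what can be claimed:

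- **TEAE table.** A reader might infer that an SAE is certain to move into the ADA-negative column. SAP 2.4.5.1 does not refer to the exclusion, so the documents show an unclear status and not a fixed misclassification.
- **Bias and its size.** A reader might infer a known bias toward no association. Any ratio would rest on invented counts. Counting event-driven draws can also bias the other way, as step 7 shows, so equal sampling per participant is a respectable reason to keep such draws out of that comparison.
- **Gaps in sampling.** Scheduled draws are 18 weeks apart from Week 12 to Week 30 and 26 weeks apart from Week 30 to Week 56. A reader might add that sampling stops at early discontinuation. The protocol calls for an early visit with EOT assessments, which include ADA, and the schedule lists ADA at EOS, 6 weeks after the last dose. Only the remaining visits up to Week 56 omit it (Section 7.1.1).
- **Frequency.** The readable protocol text sets out no SAE-triggered ADA draw. The 4- and 6-month samples apply to participants already ADA-positive at EOS. The affected group may be small.
- **Visibility.** Unscheduled ADA results and all SAEs are listed, so nothing is hidden.

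**Conclusion.** The inconsistency within SAP 2.4.5.7 is real. On the literal text, the on-study treatment-emergent ADA incidence can omit participants who meet the SAP's own definition while keeping them in the denominator. The only possible direction is understatement. The status of these participants in the TEAE and HbA1c tables is undetermined.

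The documents do not allow the effect to be computed. The percentages in steps 5 to 7 rest on assumed counts and show only that a handful of samples can matter when positives or events are few. The omission requires a participant with no positive scheduled post-baseline sample and at least one qualifying positive unscheduled sample. ADA endpoints are exploratory, descriptive and confined to the efpeglenatide arms, so the noninferiority conclusion and the hierarchical tests are unaffected. The point merits correction because immunogenicity is a safety question and the repair is small; it does not threaten the trial's main results.

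**What to change.** Replace the last sentence of the anti-drug antibody part of SAP 2.4.5.7 with wording such as:

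> Unscheduled ADA results are omitted from by-visit ADA tables. All valid post-baseline ADA samples, scheduled or not, determine participant-level ADA status, treatment-emergent ADA incidence and every table by ADA status.

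Add three items:

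1. A sensitivity version of the TEAE table by ADA status that uses scheduled samples only, so that outcome-dependent sampling can be seen.
2. A statement of how ADA samples from early EOT and pre-rescue visits are classed.
3. A statement of whether unscheduled samples enter the persistent, transient and indeterminate classes in SAP 2.1.5.1, because these depend on the number of samples and on a 16-week separation.

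The cost is a few sentences, one derivation and one additional table; the samples are already due to be listed. The small downside is that participants with events get extra chances to test positive in the main table, which the sensitivity version makes visible.
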